4.2.4.1 Subgroup Analyses for Primary Endpoint(s)

There are no subgroup analyses planned for primary endpoint.

4.3 SECONDARY ENDPOINTS ANALYSES

Secondary efficacy outcomes of response include 2 types of endpoints:

- Categorical
 - HBsAg outcomes *
 - Proportions of participants with HBsAg loss at every 12 weeks' time point
 - HBsAg seroconversion (loss of HBsAg and detection of anti-HBs antibody) over time
 - Proportions of participants with HBsAg loss (HBsAg <LLOQ) and HBV DNA <LLOQ
 - HBeAg outcomes *
 - loss of HBeAg over time
 - detection of anti-HBe antibody over time
 - HBeAg seroconversion (loss of HBeAg and detection of anti-HBe), baseline HBeAg-positive participants over time
 - Maintenance of HBV DNA levels less than lower limit of quantification (LLOQ or <20 IU/mL), <200 IU/mL and <2,000 IU/mL*)

- * Time points are as (Treatment Period: 12 weeks, 24 weeks, 36 weeks and 48 weeks; Follow-up period: 12 weeks, 24 weeks, 36 weeks and 48 weeks)
- Continuous endpoints, summarized over time
 - Quantitative HBsAg value, and its change from baseline
 - Quantitative HBV DNA value, and its change from baseline
 - Quantitative HBeAg value, and its change from baseline
 - Quantitative HBcrAg value, and its change from baseline
 - Quantitative HBV RNA value, and its change from baseline
 - Quantitative anti-HBs value
 - Quantitative anti-HBc value

Summary descriptive statistics will be used to summarize these efficacy outcome measures at each of the time points by treatment group, based on the data processing rules below.

The statistical method described for the primary endpoint is applicable for the secondary categorical endpoints, i.e. to calculate the proportion by treatment group and difference in proportion along with 95% CI's.

HBeAg / HBsAg seroconversion are defined as the loss of HBeAg / HBsAg (i.e., a negative result for HBeAg / HBsAg) and the detection of anti-HBe / anti-HBs (i.e., a positive result for anti-HBe/ anti-HBs), respectively.

The proportion of HBsAg loss, HBeAg loss, HBeAg seroconversion, HBsAg seroconversion and maintenance of HBV DNA below LLOQ, 200 and 2,000 IU/mL grouped by treatment arm will be paneled by visit (EOT, 24 weeks post-EOT and 48 weeks post-EOT) in one plot. Additional bar charts will be created, one split further by HBsAg stratification level and one split by baseline HBeAg status.

The list of required outputs and output mock shell will be covered in LoPO and output specification document respectively,

Data processing rules-

- Summary graphs of continuous endpoints will include their corresponding standard deviation or 95% CIs as appropriate
- All virology parameters (absolute and change from baseline) will be reported as Log10 (unit).
- Any BLQ or ALQ result will be imputed to the corresponding BLQ or ALQ value, respectively
- Any result reported as a ">" or "<" sign with a numerical value will be imputed to the numerical value and will be used for analyses.

- Any result reported as "TND" will be imputed to the BLQ or LoD (limit of detection) value as appropriate for each parameter.
- Only participants with quantifiable baseline results will be included in any change from baseline summary statistics.

Treatment comparison between NME's and NUC:

The mean change from baseline in HBsAg will be analyzed from analysis of covariance (ANCOVA) with treatment, visit, stratification, and treatment*visit interaction effect as fixed effect; different baseline covariates will be explored (baseline HBsAg, baseline body weight, age, genotype, baseline HBeAg status etc.) and the statistical significant baseline covariates will be included in the final model. Adjusted means and 95% CIs will be presented for each treatment arm. Difference in adjusted means for COMBO treatment Vs NUC control will be presented with 95% CIs.

The assumptions that are made using ANCOVA (that is normality of scores at treatment level, homogeneity of variance, homogeneity of regression slope, linear regression) will be assessed. A histogram of scores will be plotted for checking normality and a suitable transformation (e.g. log, square root) will be considered to correct non-normally distributed data. Leven's test will be used to test the assumption of homogeneity of variance supported by graphical presentation.

If the normality assumption is not met with any data transformation, then non parametric test will be used. The non-parametric test could be Wilcoxon rank sum test or van Elteren test.

Relationship between categorical HBsAq and baseline characteristics:

The primary efficacy parameter is the incidence of HBsAg loss (that is <0.05 IU/ml) at 24 weeks post EOT.

HBsAg will be categorized as:

HBsAg "Y": If HBsAg loss <0.05 IU/ml

HBsAg "N": If HBsAg loss >=0.05 IU/ml

The relationship between categorized HBsAg and baseline covariates will be explored using logistic regression techniques where HBsAg category(Y/N) as response and baseline covariates- age, sex, race (or country), HBV genotyping, NME combination treatments, HBeAg status, baseline HBsAg, baseline ALT, baseline DNA as independent variable. Stepwise selection option will be used to finalized the model. The independent variable will stay in the model which are significant at P<0.1.

Covariates will be checked for collinearity. Collinearity will be examined through the Variance Inflation Factor and Tolerance. Where collinearity occurs between two variables, only one of these variables will be included in the final model. An assessment of goodness of fit of the model will be performed using the Pearson Chi-Squared Goodness of Fit test, deviance test and visual inspection of index plots.

The odds ratio for independent variables will be reported along with the 95% confidence interval. If required, odds ratio will be reported by visit.

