Circulating hepatitis B core-related antigen (HBcrAg) levels provide one additional biomarker that could support demonstration of the achievement of HBV cure. HBcrAg is a composite circulating biomarker comprising HBcAg (core antigen, which is part of HBV virions), HBeAg (which arises from the same open reading frame as HBcAg and is secreted), and p22cr (precore protein). Emerging data correlate HBcrAg measurements with cccDNA levels and activity and HBV treatment outcomes (Mak et al 2018; Chen et al 2017; Inoue and Tanaka 2020; Li et al 2020). In the course of this study, a validated RUO method based on a quantitative enzyme-linked immunosorbent assay may be used to quantify HBcrAg in serum.

Antibodies against HBcAg (anti-HBc) are the first to appear during the acute phase of infection. The IgM anti-HBc levels will gradually disappear and be followed by the production of IgG anti-HBc. Novel assays for the quantification of IgG or total anti-HBc have been developed. The levels of this biomarker have been shown to vary through the different phases of the cHBV infection. They are higher during the immune clearance and reactivation phases than during the immune tolerance and inactive carrier phases. Moreover, high levels of IgG or total anti-HBc correlated with a higher rate of HBeAg seroconversion in HBeAg-positive patients treated with NUCs. In the course of this study, a validated RUO method may be used to quantify total anti-HBc in serum (Jia et al 2014; Yuan et al 2013; Fan et al 2016).

The initial participant population recruited in this study will be established on effective NUC therapy at study entry and will have circulating HBV DNA levels below the assay lower limit of quantification (defined as below 20 IU/mL) for at least 6 months, confirmed at screening. Response to therapy aiming at functional cure could potentially be modulated by HBV genotype. To determine HBV genotype in participants with undetectable HBV DNA, Sanger or deep sequencing may be attempted in some participants using amplified HBV RNA from a plasma sample collected at Day 1 or at any follow-up time point, as appropriate. *The HBV genotype may also be inferred using alternative approaches, such as serovariant determination*.

HBV DNA Monitoring

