5.1 INCLUSION CRITERIA

Participants are eligible to be included in the study only if all of the following criteria apply:

Informed Consent

 Able and willing to provide written informed consent and to comply with the study protocol according to International Council for Harmonization (ICH) and local regulations.

Age

2. Participants must be between 18 and 65 years of age, inclusive, at the time of signing the informed consent.

Weight

3. Body mass index between 18 and 32 kg/m² inclusive.

Type of Participants and Disease Characteristics

- 4. Participants with CHB infection (HBsAg positive for ≥6 months) who are on NUC (entecavir or tenofovir alafenamide/disoproxil fumarate) monotherapy for ≥12 months, having received the same NUC therapy for ≥3 months prior to screening.
- 5. HBV DNA below the LLOQ or < 20 IU/mL for > 6 months prior to screening and confirmed at screening.
- 6. Alanine transaminase (ALT) ≤1.5 x upper limit of normal (ULN) for > 6 months prior to screening, and confirmed at screening
- 7. Screening laboratory values (hematology, chemistry, urinalysis) within normal range, or judged not clinically significant by the Investigator.

Sex

8. Male and female participants:

The contraception and abstinence requirements are intended to prevent exposure of an embryo to the study treatment. The reliability of sexual abstinence for enrollment eligibility needs to be evaluated in relation to the duration of the clinical study and the preferred and usual lifestyle of the participant. Periodic abstinence (e.g., calendar, ovulation, symptothermal, or post-ovulation methods) and withdrawal are not acceptable methods of preventing fetal/embryonic drug exposure.

The following contraception requirements must be followed unless otherwise stated in the respective appendix of each treatment arm.

a) Female Participants:

A female participant is eligible to participate if she is not pregnant (see Appendix 5), not breastfeeding, and at least one of the following conditions applies:

- Woman of non-childbearing potential (WONCBP), as defined in Appendix 5.
- Woman of childbearing potential (WOCBP), who:

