1.1 OBJECTIVES AND ENDPOINTS

Table 1 Primary and Secondary Objectives and Corresponding Endpoints

Primary Objective(s)	Corresponding Endpoints
To estimate the effect of NME combination therapies on inducing a functional cure over the control arm.	% participants with HBsAg loss (loss (i.e., HBsAg <0.05 IU/mL) at 24 weeks post-EOT.
Secondary Objective(s) ^a	Corresponding Endpoints
To characterize the efficacy	% participants with HBsAg loss.
profile of NME combination therapies.	% participants with HBsAg seroconversion.
	 % participants with HBeAg loss (baseline HBeAg-positive participants).
	 % participants with HBeAg seroconversion (baseline HBeAg-positive participants).
	 % participants with HBV DNA < lower limit of quantification (LLOQ), <200 IU/mL and <2,000 IU/mL.
 To characterize the PD profile of NME combination therapies. 	 Change from baseline in quantitative HBsAg, anti-HBs, HBeAg, anti-HBe, HBcrAg, HBV RNA, and HBV DNA levels over time.
To characterize the plasma PK profiles of NMEs.	Estimated PK parameters from sparse sampling and population PK models (included below parameters but not limited to)
	Area under the curve (AUC)
	Peak Concentration (Cmax)
	Volume of distribution (Vd)
	Clearance (CL)

		Urir	ne PK
•	To assess the safety and tolerability of NME combination therapies.	•	Incidence, nature and severity of adverse events.
		•	Incidence of laboratory abnormalities based on hematology, clinical chemistry, lipids, thyroid function tests, coagulation, urinalysis test.
		•	ECGs.
		•	Vital signs including blood pressure, pulse rate, respiratory rate and body temperature.
		•	Anti-drug antibodies (ADA) (if applicable)
•	To identify presence of PK/PD relationship.	•	Analyses of PK/PD data.
•	To explore potential effects of ADA on NMEs and/or IMP, as applicable.	•	Relationship between ADA status, PK, safety, PD, and efficacy.
	Exploratory Objective(s)		Corresponding Endpoints
•	To characterize the profile of novel viral response markers.	•	Profiles and changes from baseline of total HBsAg post-dissociation of HBsAg-HBsAb complexes/components of HBsAg and quantitative anti-HBc (IgG or total).
•	To assess the relationship between baseline disease characteristics and efficacy/safety responses.	•	Association between primary and secondary outcomes and HBV genotype (obtained using HBV RNA or DNA sequencing and/or any alternative methodology, and/or from medical records prior to study entry).

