2.2 SAMPLE SIZE DETERMINATION

Approximately 30 participants will be randomized in each treatment arm. Approximately five replacement participants per arm may be replaced if participants have a dose regimen change or discontinue due to non-safety reasons. This is to ensure that the number of participants per arm of the randomized dose regimen remains close to 30.

In the event of COVID-19 or force majeure events that significantly impact compliance with the randomized dosing regimen, up to 30 additional participants may be enrolled per treatment arm to ensure that the randomized dose regimen remains close to 30. Criteria and the decision to enroll additional participants will be at the Sponsor's discretion.

The overall number of participants in this study will depend on the number of treatment arms that are included, which is not known at present.

The primary endpoint is the proportion of participants with HBsAg loss at 24 weeks post-EOT. Assuming a 3% NUC response rate, a sample size of 30 participants per arm provides 78% power to detect a pairwise 30% difference between a combination treatment arm and the NUC control arm. This is based on a two-treatment arm continuity corrected, two-sided, chi-squared test of equal proportions at a significance level of 5 %.

The sample size of combination treatment arms that achieve 30% delta for HBsAg loss at Week 48 (EOT) or follow-up Week 12 or 24 may be expanded up to approximately 100 participants. An expansion may also be triggered prior to EOT, for a treatment arm that gives an early indication of efficacy. The decision criteria to trigger an expansion arm in this case, will be documented as an appendix to the IMC/SOC charter. The expansion arm may be utilized to increase the precision of the efficacy treatment estimates; exploration of participant subgroups (e.g., baseline HBeAg status) and/or to gain additional safety data prior to Phase 3 clinical trials.

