4.1 GENERAL CONSIDERATIONS

Disposition and protocol deviations listings and summaries will be based on all randomized participants. Analysis of safety will be based on the safety population. Pharmacodynamics and efficacy analysis will be based on the modified intention-to-treat (mITT) population. Pharmacokinetic analysis will be based on PK population. Immunogenicity analysis is based on the immunogenicity population.

For the treatment arms where additional patients have been recruited to proactively mitigate any impact of COVID-19 or force majeure events, the primary analysis will be performed when approximately 30 patients considered evaluable for the primary analysis reach the primary endpoint of Week 24 post EOT. If the primary analysis is positive for an experimental treatment arm, any additional patients that have been recruited to that treatment arm, will continue and be included in the final CSR.

Evaluable patients: A patient from the mITT population will be considered 'evaluable' if no more than two consecutive siRNA missing doses due to non-safety reasons (e.g., COVID-19 disruptions). This is based on the siRNA liver half-life of ~10 weeks.

estimated from ph1 data. Therefore, after two consecutive missing doses the drug left in the liver is expected to be \sim 40%, which was considered adequate as patients would restart dosing so up to 2 missing doses are not expected to have a major impact on the efficacy.

Evaluable patients in mITT population will be used to estimate the primary endpoint/estimand.

Any subject who does not have a virology parameter evaluation during the pre-specified window for 24-week Follow-up visit (either due to missing assessment or due to early withdrawal from the study or study treatment) will be considered as a non-responder. However, if the subject with missing evaluation is a responder both before and after the visit window, then the subject will be categorized as a responder for that visit.

Key definitions:

The following definitions will be used:

Baseline: The baseline value is defined as the last available valid (quantifiable continuous or categorical value), non-missing observation for each participant prior to first study drug administration. Repeat and unscheduled assessments will be included in the derivation of the baseline values.

HBsAq Loss: HBsAg loss refers to a negative/undetectable HBsAg level, HBsAg loss is defined HBsAg levels <0.05 IU/mL.

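### The quantifiable-baseline rule in SAP 4.3 leaves the HBV DNA change-from-baseline endpoint with almost no participants, because eligibility requires unquantifiable HBV DNA

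*SAP*

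**What the plan says.** The SAP's table of objectives (Section 1.1) names the endpoint under the PD objective: "Change from baseline in quantitative HBsAg, anti-HBs, HBeAg, anti-HBe, HBcrAg, HBV RNA, and HBV DNA levels over time". Section 3 of the protocol lists it too. SAP 4.3 repeats it among the continuous secondary endpoints: "Quantitative HBV DNA value, and its change from baseline".

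The data processing rules in SAP 4.3 then do two things. One rule gives results outside the quantifiable range a number: "Any BLQ or ALQ result will be imputed to the corresponding BLQ or ALQ value, respectively". A later rule decides who enters a change summary: "Only participants with quantifiable baseline results will be included in any change from baseline summary statistics". It applies to any such summary and makes no exception for a marker.

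Protocol 5.1 sets the entry condition: "HBV DNA below the LLOQ or < 20 IU/mL for > 6 months prior to screening and confirmed at screening". Protocol 4.2.3 describes the population's HBV DNA as "below the assay lower limit of quantification (defined as below 20 IU/mL" IU/mL being the limit. SAP 4.1 defines baseline as the "last available valid (quantifiable continuous or categorical value), non-missing observation for each participant prior to first study drug administration".

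**The concern.** The eligibility rule and the analysis rule work against each other. A participant enters the trial because HBV DNA cannot be quantified, and is then left out of the HBV DNA change summary for the same reason. A secondary endpoint named in both documents would have an empty or nearly empty table.

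The few who qualify would not represent the arm. They had HBV DNA below the limit at screening and a quantifiable value before the first dose, so their later values will tend to fall back. The rest of the arm starts at the floor and can only stay there or rise. The table could therefore show a mean decline in a population where real movement is upward.

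Interim reporting is exposed as well. SAP 4.7.1 includes HBV DNA (printed there as HBC DNA) among the interim efficacy endpoints and promises change from baseline for efficacy endpoints.

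**Working it through.** The plan states no figure for the number of participants with a quantifiable HBV DNA baseline, so there is nothing to reproduce. The check has a logical step and a sizing step.

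**Logic**

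1. Entry requires HBV DNA below the LLOQ or 20 IU/mL at screening (Protocol 5.1), and Protocol 4.2.3 puts the LLOQ at 20 IU/mL.
2. Baseline is the last valid value before first dose (SAP 4.1). A quantifiable HBV DNA baseline therefore normally needs a pre-dose value of 20 IU/mL or more after a screening value below it. A value between the LLOQ and 20 could also count if an assay had an LLOQ under 20, but Protocol 4.2.3 does not describe one.
3. SAP 4.3 removes everyone else from the change summary.
4. Treating an imputed BLQ value as quantifiable does not rescue the rule. The restriction would then exclude nobody with a BLQ result and would serve no purpose.

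**Size under the rule as written**

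Inputs: N = 30 per arm (SAP 2.2: "Approximately 30 participants will be randomized in each treatment arm"); q = share with a quantifiable pre-dose value, assumed to be 0 to 10% because the documents give none.

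Expected number = N × q. Probability that the arm has nobody = (1 − q)^N. Probability of at least 2, the minimum for a standard deviation, is the binomial tail.

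| q (assumed) | Expected of 30 | Nobody | At least 2 |
|---|---|---|---|
| 0% | 0 | 100% | 0% |
| 1% | 0.3 | 74.0% | 3.6% |
| 3% | 0.9 | 40.1% | 22.7% |
| 5% | 1.5 | 21.5% | 44.6% |
| 10% | 3.0 | 4.2% | 81.6% |

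If an arm grew to 60 through the additional COVID-19 or force majeure recruitment, the expected number at q = 5% would be 60 × 0.05 = 3.0.

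**Direction of the error**

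Take a participant at 40 IU/mL on Day 1 who returns to BLQ, set to 20. The change is log10(20) − log10(40) = −0.30, and it enters the summary. Take another who starts BLQ and later reaches 2,000 IU/mL. With baseline set to 20, the change is log10(2,000) − log10(20) = +2.0, but it is excluded.

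**Size after the fix**

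With BLQ baselines set to 20 IU/mL, all of the roughly 30 participants with data enter. Values of 200, 2,000 and 20,000 IU/mL count as +1.0, +2.0 and +3.0 log10. As an illustration, if 6 of 30 reach 2,000 IU/mL and the rest stay BLQ, the mean change is (6 × 2.0 + 24 × 0)/30 = +0.40 log10. Under the current rule, none of these 30 would be counted.

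**The case against.** The strongest reply is that little information is lost. A reader might infer that the SAP misses off-treatment rebound. The documents do not support that, because the restriction covers change-from-baseline summaries only. SAP 4.3 also plans absolute HBV DNA over time in log10 units, and the proportions below LLOQ, 200 and 2,000 IU/mL at follow-up Weeks 12, 24, 36 and 48. SAP 4.5.3 plans breakthrough and relapse counts by arm with a listing, and individual ALT/virology profiles that include HBV DNA. All of these stand. Moreover, once nearly every baseline is set to 20 IU/mL, the change is the absolute log10 value minus a constant of about 1.30. That is correct, and it limits the consequence. It does not make the named endpoint reportable as written.

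Three other stronger readings also fail:

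- **That rebound seen in this trial prompted the amendment.** The protocol's summary of changes calls the revised NUC restart criteria precautionary and says they did not arise from safety findings in this study.
- **That the restriction contradicts the BLQ rule.** It does not. The BLQ rule is still needed for absolute summaries and for post-baseline values that fall below quantification. Giving a value a number and choosing who enters a summary are separate steps.
- **That the same criticism applies to HBV RNA, HBcrAg and HBeAg.** Eligibility does not force these markers below quantification. A participant already at the floor cannot show a decline, so restricting those summaries to quantifiable baselines is a defensible choice.

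The rule could also be useful for HBV DNA in a treatment-naive population, which the platform may add later. The arms now planned enrol suppressed participants, and a summary of everyone with data would still work in such an arm.

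**Conclusion.** The point holds for one endpoint. As written, the HBV DNA change-from-baseline summary would include almost no one: about 0 to 3 of 30 per arm if 0 to 10% have a quantifiable Day 1 value. That share is an assumption. The conclusion that the table is nearly empty rests on the eligibility criterion and the 20 IU/mL limit, and the assumption only sets the range. Nearly empty is the right description, because a pre-dose value of 20 IU/mL or more remains possible.

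The defect affects the final and interim change summaries for HBV DNA. The primary endpoint and the 30% interim criterion rest on HBsAg loss and are unaffected. The trial is exploratory and its analyses are descriptive, so no formal inference is at risk. It is still worth correcting, since a secondary endpoint named in both documents cannot be meaningfully reported under the current rule and the correction is nearly free.

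**What to change.** In the SAP 4.3 data processing rules, exempt HBV DNA from the quantifiable-baseline restriction. Set a BLQ baseline to the LLOQ, as the existing BLQ rule provides, and summarise log10 change in all mITT participants with data. Apply the same rule to the interim summaries in SAP 4.7.1. Add a few words to the baseline definition in SAP 4.1 so that a BLQ result counts as a valid HBV DNA baseline; otherwise its reference to quantifiable values could bring the exclusion back.

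For every marker with a change summary, report by arm the number of participants with a quantifiable baseline. The restriction may stay for HBV RNA, HBcrAg and HBeAg.

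The cost is a few lines of SAP text and some extra table entries. No new data, visits or sample size are needed. Dropping the HBV DNA change summary and relying on the absolute values and threshold proportions would also remove the inconsistency, but the endpoint lists in both documents would then have to change.

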1.2 STUDY DESIGN

This study is designed to be adaptive to open additional shorter duration treatment arms or to expand existing treatment arms for NME combination therapies that show promising efficacy outcomes. The platform design also has the flexibility to open new treatment arms to explore different combination regimens or different patient populations pending new submission and HA/EC approval. Based on emerging data and/or company prioritization of assets, treatment arms may be terminated early or not opened for randomization or certain NMEs in the combination treatment arm might be terminated

^a Efficacy and PD endpoints are assessed at every 12-week time point.

while therapy is maintained with the remaining NMEs. The Sponsor will notify the Investigator and HA/EC if the study or certain treatment arms or certain NMEs are placed on hold, or if the Sponsor decides to discontinue certain treatment arms or certain NMEs.

Treatment arms may be staggered relative to other treatment arms in order to increase study efficiency with regards to timely interim data readouts or to reduce the complexity of study conduct. For the first combination, participants will be randomized on Day 1 to an NME combination arm (N=30) or the control arm (N=30) using an adaptive stratified sampling method, stratified at screening HBsAg level (< 1,000 IU/mL, ≥ 1000 IU/mL), with a minimum of 12 participants per arm with a screening HBsAg level of < 1000 IU/mL. For NME combination arms that will be introduced later into the platform study, the allocation ratio of participants to the control arm, will depend on the number of actively enrolling arms with the stipulation that no more than 17% of participants will be randomly allocated to a control arm. Additionally, for subsequent arms the proportion of patients with HBsAg level < 1000 IU/mL, ≥ 1000 IU/mL within each treatment arm, will be maintained as closely as possible to the first combination treatment and the NUC control arm (first set of enrollments).

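### The HBsAg change-from-baseline ANCOVA stacks visits with no within-participant correlation and keeps covariates by significance, so its covariate tests and any visit-averaged confidence interval are anti-conservative

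*SAP*

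**What the plan says.** The model is in SAP 4.3, in the part comparing the NME combinations with NUC: "analysis of covariance (ANCOVA) with treatment, visit, stratification, and treatment*visit interaction effect as fixed effect; different baseline covariates will be explored". The candidate covariates are "baseline HBsAg, baseline body weight, age, genotype, baseline HBeAg status etc", and "the statistical significant baseline covariates will be included in the final model". No significance threshold is given for this model.

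Two outputs are promised: "Adjusted means and 95% CIs will be presented for each treatment arm", and "Difference in adjusted means for COMBO treatment Vs NUC control will be presented with 95% CIs". Neither sentence names a visit. Under SAP Table 1, "Efficacy and PD endpoints are assessed at every 12-week time point". SAP 4.3 lists eight such points for the categorical endpoints: four on treatment and four in follow-up.

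The assumptions to be checked are normality, equal variance, equal slopes and linearity. Independence of observations is not among them. On variance, "Leven's test will be used to test the assumption of homogeneity of variance", but no action follows if it fails. The fallback applies only when normality cannot be achieved: "The non-parametric test could be Wilcoxon rank sum test or van Elteren test".

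**The concern.** A model with visit and treatment-by-visit effects uses one row per participant per visit. Rows from the same person are correlated. If the errors are treated as independent, the residual degrees of freedom count rows instead of people, and anything estimated between participants looks too precise. Two outputs fall in that class: the test of a baseline covariate, and a treatment difference averaged over visits.

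The covariate test matters because it decides the final model. Even baseline HBsAg, the obvious adjuster for change in HBsAg, has to pass it. The averaged difference matters because a single adjusted mean per arm is a natural reading of the text. An interval labelled 95% that covers far less often would overstate how precisely the combination-versus-NUC difference is known.

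**Working it through.** **The plan's own figure.** The documents give no precision or power figure for this ANCOVA. The only stated figure is the 78% power for the binary primary endpoint (SAP 2.2: 30 per arm, 3% versus 33%, two-sided 5%, continuity-corrected). Inverting the continuity correction, n = (m/4)·[1 + √(1 + 4/(0.30·m))]² with n = 30 gives m = 23.7, and power at m is 78.6%. The figure is reproduced, and the present issue does not affect it.

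**Inputs.** From the SAP: 30 per arm; at least 12 per arm in the low-HBsAg stratum (12 used in the cross-check below); fixed effects as stated; T = 8 visits, or T = 4 if only on-treatment points are used. Assumed: within-participant correlation ρ of 0.5 to 0.9 with equal correlation between visits, and a retention threshold of 0.05.

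**Formula.** For a contrast averaged over T visits, the independent-error variance is 2σ²/(nT). The true variance is 2σ²[1 + (T−1)ρ]/(nT). The standard error is therefore too small by f = √[1 + (T−1)ρ]. Approximate coverage is 2Φ(1.96/f) − 1, and the approximate size of a 5% covariate test is 2[1 − Φ(1.96/f)]. Example: T = 8, ρ = 0.5 gives f = √4.5 = 2.12, coverage 64.4% and size 35.6%.

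**Simulation of the model as written** (ordinary least squares, 20,000 runs):

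| Visits | ρ | f | Averaged 95% CI coverage | Null covariate p<0.05 |
|---|---|---|---|---|
| 8 | 0.5 | 2.12 | 63.6% | 35.7% |
| 8 | 0.7 | 2.43 | 58.0% | 42.0% |
| 8 | 0.9 | 2.70 | 52.2% | 47.6% |
| 4 | 0.5 | 1.58 | 78.6% | 22.0% |
| 4 | 0.7 | 1.76 | 73.4% | 27.3% |
| 4 | 0.9 | 1.92 | 68.2% | 31.1% |

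A cross-check with 1,500 runs per scenario and five null covariates in the model agrees. At ρ = 0 with 8 visits it returns 95.2% coverage and 5.0% size, as it should. At ρ = 0.3 with 8 visits, coverage is already down to 71.3%. With AR(1) correlation of 0.8 and 8 visits it is 61.2%.

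**Covariate selection.** With five null candidates, 8 visits and ρ = 0.5/0.7/0.9 (4,000 runs), at least one is kept in 89.4/94.2/95.7% of trials. A valid test would give about 1 − 0.95⁵ = 22.6%; the simulated range is about 21% to 24%.

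**Visit-specific differences.** Here the naive and true variances are both 2σ²/n when variances are equal across visits, so coverage should hold. At 8 visits it is 94.8/94.7/94.3%, falling to 93.8/93.1/92.5% after the covariate selection.

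**Unequal variances (illustration only; the documents give no SD).** Let the SD rise in equal steps from 0.5 to 1.0 log10 over 8 visits in both arms, with ρ = 0.8. The pooled SD is √0.589 = 0.768. Approximate coverage is 2Φ(1.96 × 0.768/0.5) − 1 = 99.7% at the first visit and 2Φ(1.96 × 0.768/1.0) − 1 = 86.8% at the last. Simulation (3,000 runs) gives 99.7% and 86.5%.

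**Analysis that respects participants** (one ANCOVA per visit, or on participant means): averaged coverage 94.8% to 95.4%, and mean visit-specific coverage 94.7% to 95.1%.

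**The case against.** The strongest reply is that the worst figures belong to a contrast the SAP never explicitly says it will report. SAP 4.3 summarises continuous endpoints over time, treatment-by-visit is in the model chiefly to yield visit-level differences, and Wilcoxon or van Elteren tests suit one value per participant at a visit. By-visit reporting is the likelier reading, and on it coverage is close to nominal. The output list and mock shells, which are not available here, may settle the point. A programmer may also add a repeated term under the ANCOVA label.

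Other limits are fair. The correlation and the 0.05 threshold are assumed. Eight visits is the upper case, since the visit list is attached to the categorical endpoints and the PD-L1 LNA arms treat for only 24 or 36 weeks. The HBsAg stratum always stays in the model, so adjustment for HBsAg level does not rest wholly on the significance screen. Everything here is descriptive.

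These points limit the size of the harm but do not remove the defect. The selection rule is explicit, and it runs on a test that is invalid for any positive within-participant correlation, whichever contrast is reported. Output shells can fix the choice of visit; they cannot supply a covariance structure or repair the rule. Even with a valid test, screening five null covariates would keep at least one in about a fifth of trials.

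**Conclusion.** The concern holds. As written, the covariate tests are invalid. If a visit-averaged difference is reported from 8 visits, its interval is too narrow by a factor of 2.1 to 2.7 and covers 64% down to 52% of the time; with 4 visits, 1.6 to 1.9 and 79% down to 68%. These sizes rest on an assumed correlation of 0.5 to 0.9, but the direction holds for any positive value. Visit-specific intervals lose little when variances are similar (94% to 95%, or 92.5% to 94% after selection) and can be off in either direction when variances change over time.

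This should be corrected, but it is not a threat to the trial's main conclusion: the CMH primary analysis, the 30% rule and the power calculation do not depend on it.

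**What to change.** Replace the paragraph in SAP 4.3 with a mixed model for repeated measures:

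- Participant as the repeated subject, with unstructured covariance and a named order of fallback: heterogeneous Toeplitz, then AR(1) with robust standard errors. Use Kenward-Roger degrees of freedom where applicable.
- Fixed effects for treatment, visit, treatment-by-visit, stratum, baseline log10 HBsAg and baseline-by-visit, all pre-specified. Delete the significance-based covariate selection.
- A statement that adjusted means and differences are reported by visit, at EOT and follow-up Weeks 24 and 48.
- Arm-specific variances only if estimable: 8 visits need 8 × 9/2 = 36 covariance parameters, or 72 if separate by arm.

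A separate ANCOVA at each visit with pre-specified baseline would also deal with the correlation.

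The cost is one paragraph and standard software, with no new data; convergence may force the fallback. With 8 visits, an averaged contrast would have an interval about 2.2 to 2.8 times wider, which is its proper width. Visit-specific intervals change by 2% to 3% under equal variances and may narrow or widen otherwise (0.67 to 1.33 times in the illustration). The change does not address the floor created by setting values below quantification to the limit.
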